6.1.2. Sample Size Re-Estimation	38
6.1.3. Pharmacokinetic Analysis	38
6.2. Site Level Unblinding	38
6.3. Sponsor/Trial Level Unblinding	39
7. References	40

Table of Contents

Table	Page
Table GBGC.5.1. Analysis Populations for Study H9X-MC-GBGC.....	19
Table GBGC.5.2. Thresholds for Determining Abnormal Systolic Blood Pressure, Diastolic Blood Pressure, and Pulse Rate.....	30
Table GBGC.5.3. Thresholds for HR, PR Interval, and QTc Interval.....	31

List of Figures

Figure		Page
Figure GBGC.5.1.	Illustration of study design for Study H9X-MC-GBGC.....	13
Figure GBGC.5.2.	Graphical testing scheme for Study H9X-MC-GBGC.	18

3. Revision History

Version 1 of this statistical analysis plan (SAP) was approved before the protocol was finalized for the purpose of sharing with the Food and Drug Administration (FDA) in a Type C meeting.

Version 2 reflected changes made to align the SAP with changes made to the draft protocol prior to sharing it with the FDA.

Version 3 of the SAP reflected changes made to address the FDA's feedback received from the above Type C meeting. More details were included regarding the sample size re-estimation (SSR) and analyses to address missing data.

Version 4 of the SAP reflected changes made to address the FDA and the European Medicines Agency's (EMA's) feedback regarding the study design and the statistical methods and aligned with the approved amended protocol H9X-MC-GBGC(a). It provided additional clarity and some necessary modifications and addressed graphical approach testing scheme to control Type 1 error among multiple comparisons of interest. It was approved prior to the study initiation to maintain *a priori* status for the SAP.

The overall major changes and rationale for the changes incorporated in Version 4 are summarized below:

1. To reflect the changes made in the protocol:
 - a. Added study design diagram, dulaglutide 0.75 mg and 1.5 mg pooled analysis in primary and key secondary objectives to evaluate change from baseline in hemoglobin A1c (HbA1c), body mass index (BMI), fasting blood glucose (FBG) to Week 26 and HbA1c target of $\leq 6.5\%$ at Week 26 in Section 4, Sections 5.1 to 5.3, and Sections 5.11 and 5.12.
 - b. Changed randomized subjects per arm from 75 to 50, replaced 4* with 6 \times in SSR formula, and added Bayesian approach as sensitivity analysis for SSR assessment in Section 5.1.
 - c. Removed "patient as a random effect" from all mixed-effects model for repeated measures (MMRM) models and added appropriate estimate statement to form dulaglutide pooled arm effect and comparison between dulaglutide pooled and placebo arms; moved autoregressive as an option after Toeplitz to a new row in Section 5.2.
 - d. Replaced gatekeeping testing strategy with graphical approach in Section 5.3.
 - e. Added health outcome addendum population, and revised per protocol, completer set populations definition restricted to Week 26 in Section 5.4.
 - f. Changed external statistical analysis center (SAC) to internal SAC but external to study team in Section 6.1.
2. Changed "intent-to-treat (ITT) estimand" to "treatment regimen estimand" in this entire document.
3. Added statistical analysis visit window rational and definition.
4. Rearranged Sections 5.11 and 5.12.

5. Added graphical approach testing scheme allowing further change after blinded evaluating the correlation matrix at Week 26 among change from baseline in HbA1c, FBG, and BMI in pediatric patient population prior to datalock in Section 5.3.
6. Added analysis for adverse events (AEs) including but not limited to AE, treatment-emergent adverse events (TEAEs), serious adverse events (SAEs), hyperglycemia requiring rescue, vital signs, electrocardiogram (ECG), injection site reaction, allergic/hypersensitivity, and pubertal progression as a new Section 5.15. Added stratified Wilcoxon rank sum test as sensitivity analysis for hypoglycemia rate, which will be used as the primary analysis only if the negative binomial regression analysis fails to converge in Section 5.15.3. Re-organized analysis of laboratory analytes in details in Section 5.15.8.
7. Added all exploratory analysis in a stand-alone Section 5.16.
8. Added patient-reported outcome (PRO) analysis in Section 5.18.

Version 5 of the SAP reflects changes made to address the regulatory agencies' feedback on the approved protocol H9X-MC-GBGC(a) and SAP Version 4.0. The key changes are summarized below:

- EMA
 1. The primary analysis population for the primary objective for EMA is changed to the ITT population excluding those patients treated with diet and exercise only who are metformin naïve (Sections 5.3 and 5.11.1).
 2. Add ITT population by excluding metformin naïve patients for EMA in Section 5.4.
- FDA
 1. Delete paragraph regarding estimands and graphical approach from Section 5.2.
 2. Add Section 5.11.3 "Multiple Imputation for Missing Data" by moving "tipping point" approach to this section. Update "copy reference" using all nonmissing rescued subject data as reference to do imputation for all missing data within the same treatment. The observed nonmissing data and imputed data for the observed missing ones will be evaluated using analysis of covariance (ANCOVA) model. This result will be implemented in graphical approach for multiplicity adjustment (Sections 5.3).
 3. Add descriptive summary for the primary and key secondary endpoints using 14 years old as cutoff points (≤ 14 , > 14) and update age cutoff of "==" sign going with "<" in Sections 5.17 and 5.18.
 4. Adverse event of interest is reorganized by moving "hypoglycemia" to Section 5.15.2.1; add "Renal Impairment" summary under Section 5.15.2.6; and moving out "Anti-drug Antibodies (immunogenicity)," "major cardiovascular events," "malignant events," to Sections 5.15.3, 5.15.4, and 5.15.5, respectively.
 5. Add analyses for the pharmacodynamics biomarkers to evaluate insulin sensitivity and beta-cell function in Section 5.16.6. The pharmacodynamics secondary biomarker visit window is added as an entry into Table GBGC.8.1.

Version 6 of the SAP reflects changes made to update the graphical testing scheme, to add a criterion to exclude patients from the per protocol (PP) population, to remove the appendix Table GBGC.8.1 with the analysis windows, and to remove the Bayesian approach for sample size re-estimation. The key changes are summarized below:

1. Add the pooled arm comparison with placebo for FBG, BMI, and HbA1c target of $\leq 6.5\%$ analyses in the graphical testing scheme since these are key secondary objectives. Rearrange the testing order, putting the testing of FBG before BMI, and BMI before HbA1c target of $\leq 6.5\%$ to maximize the overall trial success rate.
2. Add 1 criterion to exclude patients from PP population: “Patients that use systemic glucocorticoids for more than 14 days,” since this is a standard criterion to exclude patients from the PP population in adult dulaglutide studies.
3. Remove the appendix of the analysis windows. Will use the actual visit as collected.
4. Remove the Bayesian approach for the sample size re-estimation.

Version 7 of the SAP reflects changes made to add a primary database lock. The following key changes were made to align the SAP with amendments to the protocol or protocol addenda.

1. Updated key secondary, other secondary, and exploratory objectives.
2. Updated plasma glucose (PG) level for hypoglycemia from ≤ 70 mg/dL to <70 mg/dL for both safety analyses and exploratory efficacy analyses of composite endpoints.
3. Added that “Based on regulatory feedback, the sample size re-estimation was performed in 2019 and confirmed the original sample size estimation, suggesting that approximately 150 patients be enrolled.”
4. Removed the completer set (CS) population and removed analyses for CS and PP populations.
5. Defined HbA1c strata in the models using baseline HbA1c.
6. Removed the following sensitivity analyses: ANCOVA with last observation carried forward (LOCF) and tipping point approach.
7. Removed the Chi-square test to use Fisher’s exact test only.
8. For the treatment regimen estimand, changed the primary analysis model from MMRM to ANCOVA with multiple imputation (MI) for change from baseline in HbA1c, FBG and BMI; removed analyses without MI.
9. Removed the baseline HbA1c-by-visit interaction from the longitudinal logistic regression model for HbA1c target for efficacy estimand.
10. Changed the primary analysis model from longitudinal logistic regression to logistic regression for HbA1c target $<7.0\%$ for the treatment regimen estimand.
11. Replaced country subgroups with region subgroups (US vs non-US).
12. Added a primary database lock at 26 weeks; clarified that PK team external to the study team may gain access to the unblinded data during the double-blind phase prior to the primary database lock.

In addition, the following key changes were made to the SAP only:

13. Changed the primary analysis model from ANCOVA to MMRM for change from baseline in FBG for the efficacy estimand since FBG is a longitudinal measurement.
14. Updated the summary of related AEs to be for AEs related to the study treatment since AEs related to the study treatment instead of other reasons are more relevant to safety concerns.
15. Removed sections for clinical trial registry analyses since they are not relevant for the clinical study report (CSR).
16. Updated that the listing of patients with severe, persistent hyperglycemia will be generated for patients who received rescue therapy since investigators were to prescribe rescue therapy for this reason which is the data collected on the case report form.
17. Removed laboratory analyses by visit since this level of detail is not expected to be insightful.
18. Removed hypoglycemia analyses for asymptomatic, nocturnal, and probable hypoglycemia events since they are already included in total hypoglycemia analyses, and added an additional hypoglycemia analysis, which will report all hypoglycemia events with PG <54 mg/dL, regardless of symptoms, and all severe hypoglycemia episodes for the ITT population, including events that occurred after patients started rescue therapy, since this was requested by FDA in other studies.
19. Clarified that subgroup analyses will be performed for the treatment regimen estimand only.
20. For baseline HbA1c ($\leq 8.0\%$, $>8.0\%$) subgroup analysis, added back the baseline HbA1c to the model as a covariate so that the results for actual and change from baseline are consistent, and the model terms are consistent within subgroup analyses.
21. Streamlined PRO section to reflect the latest user guide.
22. Removed the section specifying major cardiovascular events as an AE of interest since it was not included in the protocol as such, and the reporting of these events in this study population is unlikely. Any cardiovascular events that do occur should be reported as AEs and will be included in the analysis of TEAEs.
23. Updated the graphical testing scheme based on relevance of endpoints to clinicians and simulations using blinded data and published results from other trials.
24. Based on FDA feedback, the copy reference approach for multiple imputation for the primary analysis based on the treatment regimen estimand was changed to the washout method.
25. Based on FDA feedback, an interaction term of treatment by baseline insulin use was added to the negative binomial model for the analysis of hypoglycemia rates. In addition, the analyses for the incidence of hypoglycemia episodes and hypoglycemia rates will be conducted separately for the subsets of patients using insulin versus those not using insulin at baseline.

4. Study Objectives

4.1. Primary Objective

The primary objective of this study is to test the hypothesis that dulaglutide (0.75 mg and 1.5 mg, pooled) given subcutaneously once a week for 26 weeks to children and adolescents with type 2 diabetes mellitus (T2DM) who have inadequate glycemic control, despite diet and exercise, with or without metformin and/or basal insulin is superior to placebo in the treatment of T2DM, as measured by baseline to Week 26 change in HbA1c.

4.2. Secondary Objectives

The secondary objectives of the study are to assess the efficacy, safety, pharmacokinetics (PK) and pharmacodynamics (PD) of dulaglutide in patients.

The key secondary efficacy objectives are to compare dulaglutide 0.75 mg and dulaglutide 1.5 mg arms (individually and pooled) to placebo with respect to the following parameters:

- Change in HbA1c between baseline and Week 26 (individual doses only)
- Change in FBG between baseline and Week 26
- Percentage of patients with HbA1c <7.0% at Week 26 (ADA 2020)
- Change in BMI between baseline and Week 26

The other secondary efficacy objectives are to assess the 2 dulaglutide treatment groups (individually and pooled) with respect to the following parameters:

- Change in HbA1c between baseline and Week 52
- Change in FBG between baseline and Week 52
- Percentage of patients with HbA1c <7.0% at Week 52
- Change in BMI between baseline and Week 52

The secondary safety objectives are to compare the dulaglutide 0.75 mg and dulaglutide 1.5 mg arms (individually and pooled) to placebo with respect to the following parameters at 26 weeks, and to assess the following parameters in dulaglutide 0.75 mg and dulaglutide 1.5 mg arms (individually and pooled) at Week 52:

- Glucose management-related safety assessed by the incidence of self-reported hypoglycemic events and the incidence of patients requiring rescue for severe, persistent hyperglycemia.
- Pancreatic safety assessed by the incidence of cases of pancreatitis confirmed by adjudication and the effect on pancreatic enzymes.
- Thyroid-related safety assessed by the incidence of cases of thyroid TEAEs and effect on serum calcitonin.

- Immune system-related safety, including the incidence of dulaglutide anti-drug antibodies (ADAs) and the incidence of allergic and hypersensitivity reactions, and injection site reactions.

The secondary PK/PD objective is as follows:

- Characterization of the PK of dulaglutide and the relationship between dulaglutide exposure and key safety and efficacy measures.

4.3. Exploratory Objectives

The exploratory objectives are to compare the dulaglutide 0.75 mg and dulaglutide 1.5 mg arms (individually and pooled) to placebo with respect to the following parameters at 26 weeks, and to assess the following parameters in the dulaglutide 0.75 mg and dulaglutide 1.5 mg arms (individually and pooled) at Week 52 (unless otherwise specified):

- Percentage of patients with HbA1c $\leq 6.5\%$ at Weeks 26 and 52
- Change in HbA1c between baseline and Week 13
- Percentage of patients having HbA1c $\leq 6.5\%$ without severe, documented symptomatic (<70 mg/dL), or probable hypoglycemic episodes at Weeks 26 and 52
- Percentage of patients having HbA1c $< 7.0\%$ without severe, documented symptomatic (<70 mg/dL), or probable hypoglycemic episodes at Weeks 26 and 52
- Change in weight between baseline and Weeks 26 and 52
- Change in hormone-related safety assessed by the effect on morning serum prolactin, insulin-like growth factor-1 (IGF-1), estradiol, testosterone (males only), luteinizing hormone (LH), and cortisol between baseline and Weeks 26 and 52
- Change in serum lipids between baseline and Weeks 26 and 52
- Change in Tanner staging between baseline and Weeks 26 and 52
- Change in BMI standard deviation score (SDS) between baseline and Weeks 26 and 52
- Change in height and height SDS between baseline and Weeks 26 and 52
- Change in waist circumference between baseline and Weeks 26 and 52
- Change in the EQ-5D-Youth version (EQ-5D-Y) visual analogue scale (VAS) score between baseline and Weeks 26 and 52
- Percentage of patients reporting each level of problem on each dimension of the EQ-5D-Y at baseline and Weeks 26 and 52
- Assess effect of dulaglutide on measures of insulin resistance, beta cell function, and serum adiponectin at Weeks 13 and 26

- Change in basal insulin dose from baseline to Week 26 and from baseline to Week 52

5. A Priori Statistical Methods

Study H9X-MC-GBGC (GBGC) is a Phase 3, multicenter, randomized, double-blind, parallel-arm, placebo-controlled superiority trial with an open-label extension (Figure GBGC.5.1). A minimum of 150 male and female children and adolescents (ages 10 to <18 years) with T2DM and inadequate glycemic control on diet and exercise alone or diet and exercise plus metformin and/or basal insulin will be enrolled. Randomization will be stratified by the patient's background therapy and screening HbA1c. There will be a limitation on the number of patients with inadequate glycemic control managed by diet and exercise alone who have not previously received metformin so that these patients constitute no more than 25% of the total number of completers. The sponsor may place limitations on the patients enrolled depending on their demographics to meet regulatory expectations.

The main study has 4 periods: (1) a screening period lasting up to 4 weeks; (2) a double-blind treatment period lasting 26 weeks; (3) an open-label extension period lasting 26 weeks; and (4) a 30-day safety follow-up period.

[figure not shown]

Figure GBGC.5.1. Illustration of study design for Study H9X-MC-GBGC.

5.1. Determination of Sample Size

Approximately 150 patients will be enrolled (50 patients per arm), in order to obtain 120 completers assuming a dropout rate of 20%. This provides at least 90% power for demonstrating superiority of the pooled dulaglutide 0.75 mg and 1.5 mg arms to placebo (primary objective) assuming a difference in mean change from baseline in HbA1c of -0.65% and standard deviation (SD) of 1%. Under the same assumptions, each individual dulaglutide arm will have at least 80% power to demonstrate superiority over placebo. The screen failure rate is estimated as 80%. Approximately 750 patients will be screened.

Because of the high degree of uncertainty regarding the appropriate sample size, the SAC may perform an SSR after approximately 100 patients have been enrolled. Based on treatment variability only (not treatment effect), the SAC may advise an increase in sample size up to approximately 189 patients enrolled (63 per arm) in order to obtain 150 completers. This new sample size would provide at least 80% power for demonstrating superiority of the pooled dulaglutide 0.75 mg and dulaglutide 1.5 mg arms to placebo with a difference in mean change from baseline in HbA1c of -0.65% and SD of 1.3% assuming a dropout rate of 20%. Under the same assumptions, each individual dulaglutide arm will have at least 69% power to demonstrate superiority to placebo.

Because of the anticipated difficulties in enrollment and the necessity for meeting regulatory timelines, Eli Lilly and Company (Lilly) will ultimately decide whether to conduct this SSR after taking into consideration the study enrollment rate and other factors. This calculation will not require input from the Data Monitoring Committee (DMC). The SAC will provide a brief communication to the Lilly Study Team indicating only the recommended sample size (up to approximately 189 patients). Lilly will then have the ability to adopt the recommended sample size or stick to the original sample size if it is determined to be too challenging to enroll or there are other feasibility concerns. No alpha adjustment is necessary for this analysis as it does not increase Type 1 error (Mehta and Tsiatis 2001; Pritchett et al. 2011).

To re-estimate the SD, a MMRM analysis of the change from baseline in HbA1c using restricted maximum likelihood (REML) will be used. This model will be fitted with baseline HbA1c as a covariate, stratification factors (insulin usage, metformin usage), treatment, visit, and treatment-by-visit interaction as fixed effects. An unstructured covariance structure will be used to model the variability. The Kenward-Roger method will be used to estimate the denominator degrees of freedom. The analysis model incorporates treatment and treatment-by-visit interaction terms to ensure accurate calculation of the total SD. However, the only output from this analysis will be the SD at Week 26 if variance-covariance is unstructured. No information on the observed treatment difference will be reported since it will not be utilized to determine the recommended sample size. The estimated SD is denoted as $\hat{\sigma}$. The dropout rate will not be reassessed during the assessment of the variability. The assumed value of 20% (0.2) in the initial power calculation will be used. The dropout rate is denoted as f . Based on the estimated variability and the assumed dropout rate, the recommended sample size, \hat{N} , is estimated using,

$$\hat{N} = 6 \times \frac{(Z_{1-\alpha} + Z_{1-\beta})^2}{(\mu/\hat{\sigma})^2} \left(\frac{1}{1-f} \right)$$

with $\alpha = 0.025$ (one-sided), $\beta = 0.2$, $\mu = -0.65\%$, $f = 0.2$, and Z representing the standard normal quantiles.

The allowable range of the total sample size is constrained in a pre-specified manner, subject to an approximate minimum N_{\min} of 150 and maximum sample size N_{\max} of 189 patients. If the recommended sample size is greater than N_{\max} , then N_{\max} will be used. If the estimated final sample size is less than N_{\min} , then N_{\min} will be used. The SSR procedure was evaluated via simulation and is efficient in determining the appropriate sample size under a range of possible scenarios without inflating Type 1 error. No alpha adjustment to the final analysis is planned whether or not the sample size is increased.

Based on regulatory feedback, the sample size re-estimation was performed in 2019 and confirmed the original sample size estimation, suggesting that approximately 150 patients be enrolled. This figure is based on an estimated HbA1c SD of 1.4% provided by the SAC and assumed treatment difference of -0.8% and assumed proportion of patients with missing HbA1c measurement at 26 weeks equal to 10%.

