Additional secondary efficacy endpoints are the following:

- Change in FBG between baseline and Week 26 and Week 52
- Percentage of patients achieving a target HbA1c <7.0% at Week 26 and Week 52
- Change in BMI from baseline to Week 26 and Week 52
- Change in HbA1c measured in the central laboratory from baseline to Week 26 and Week 52

Safety: Secondary safety endpoints include:

- Incidence of hypoglycemic episodes and the need for rescue due to hyperglycemia at Weeks 26 and 52
- Incidence of pancreatitis and change from baseline in pancreatic enzymes to Weeks 26 and 52
- Incidence of thyroid TEAEs and change from baseline in serum calcitonin to Weeks 26 and 52
- Incidence of dulaglutide ADAs and the incidence of allergic, hypersensitivity, and injection site reactions at Weeks 26 and 52

Pharmacokinetics: Venous blood samples to measure the plasma concentrations of dulaglutide using validated bioanalytical assays.

Pharmacodynamics: Endpoints may include, but are not necessarily limited to, endpoints for efficacy (HbA1c, glucose) and safety (blood pressure, heart rate). The relationship between dulaglutide dose and/or concentration and safety and efficacy measures and patient or study factors that may influence PK or PD responses will be performed using all available patient data.

Health Outcomes: To compare the effect of dulaglutide compared to placebo on health status, as measured by the change from baseline to Week 26 and to assess the following at Week 52 in the validated patient-reported outcome (PRO) measure, EQ-5D-Y.

Statistical Methods:**Determination of Sample Size:**

A sample size of approximately 150 will be enrolled (50 patients per arm), in order to obtain 120 completers at 26 weeks. This sample size provides at least 90% power for demonstrating superiority of the pooled dulaglutide 0.75 mg and 1.5 mg arms compared to placebo (primary objective), with a mean difference in change from baseline in HbA1c of -0.65% and standard deviation of 1%, assuming a dropout rate of 20%. Under the same assumptions, each individual dulaglutide arm will have at least 80% power to demonstrate superiority over placebo. The screen failure rate is estimated as 80%. Among the completers, there will be no more than 25% of patients who, at baseline, were treated with diet and exercise only and who are metformin naïve.

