The screen failure rate is estimated as 80%. Approximately 750 patients will be screened, depending on the total enrolled. Based on regulatory feedback, the sample size re-estimation was performed in 2019 and confirmed the original sample size estimation suggesting that approximately 150 patients be enrolled.

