There may be 2 database locks for this study. A primary database lock may be conducted for all data accumulated through the time when all randomized patients have completed 26 weeks of treatment (Visit 9, primary objective endpoint). The final database lock will be conducted for all data accumulated through the time when all patients have completed the 4-week Safety Follow-Up Period (through Visit 801). Following the primary database lock, the sponsor will be unblinded to analyze and report the data.

12.2.11.1. *Safety Analysis*

The DMC will conduct a safety interim analysis approximately every 6 months until all patients have reached the primary endpoint at 26 weeks as soon as a total of 50 patients are enrolled. The number of interims may be adjusted by the actual enrollment rate.

12.2.11.2. *Sample Size Re-Estimation*

After 100 patients have been enrolled, an information-based sample size re-estimation (SSR) calculation may be conducted by the SAC. Only the variability of the primary endpoint will be used in this calculation. No alpha adjustment is needed. The details of the SSR are included in the SAP.

12.2.11.3. *Initiation of Pharmacokinetic Analyses*

A limited number of pre-identified individuals may gain access to the unblinded data prior to the primary database lock at Week 26, in order to initiate the PopPK/PD model development processes. After the final database lock, PK and PK/PD data may be analyzed graphically or used to refresh the PopPK and PK/PD models developed at primary database lock. Information that may unblind the study during the analyses will not be reported to study sites or blinded study team until the study has been unblinded.

13. Informed Consent, Ethical Review, and Regulatory Considerations

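### At the SAC's SD of 1.4% the re-estimation rule in SAP 5.1 returns the 189 cap, so the 2019 exercise did not confirm 150; the only power stated for 150 still assumes SD 1.0%

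*SAP*

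**What the plan says.** The rule is variance-only in both documents. Protocol 12.2.11.2 says: "Only the variability of the primary endpoint will be used in this calculation". SAP 5.1 says: "Based on treatment variability only (not treatment effect), the SAC may advise an increase in sample size". SAP 5.1 then prints the formula with one-sided α = 0.025, 80% power, a difference of -0.65% and a dropout fraction of 0.2, and bounds the result between 150 and 189. It rules out updating dropout: "The dropout rate will not be reassessed during the assessment of the variability", and "The assumed value of 20% (0.2) in the initial power calculation will be used".

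The sponsor keeps discretion over the outcome: "Lilly will then have the ability to adopt the recommended sample size or stick to the original sample size" if enrollment or feasibility makes an increase too difficult.

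The 2019 result is reported in Protocol 12.1 as having "confirmed the original sample size estimation suggesting that approximately 150 patients be enrolled", with no inputs shown. SAP 5.1 makes the same statement and adds the inputs: "This figure is based on an estimated HbA1c SD of 1.4% provided by the SAC and assumed treatment difference of -0.8"%, with 10% of patients assumed to have no Week 26 HbA1c.

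On power, the Protocol Synopsis says: "This sample size provides at least 90% power for demonstrating superiority of the pooled dulaglutide 0.75 mg and 1.5 mg arms compared to placebo", at a difference of -0.65%, SD 1% and 20% dropout, with at least 80% for each dose. Protocol 12.1 and SAP 5.1 repeat this.

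**The concern.** The 2019 calculation changed two inputs that the rule holds fixed, and did so in the same section that fixes them. Neither document says that this departed from the rule. A reader of Protocol 12.1, which shows no inputs, would conclude that the trial's own variance estimate supported 150 patients under the written algorithm.

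The SAC's SD is 40% above the planning value (1.4 against 1.0). Unless the other inputs move, that raises the required sample size by a factor of 1.4² = 1.96. Yet the only power printed for 150 patients is still the one at SD 1.0%.

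The SAP's case for no alpha adjustment comes with a re-estimation that leaves the treatment effect out. Where the treatment difference is then changed, its origin should be stated.

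**Working it through.** **Inputs.** From SAP 5.1: α = 0.025 one-sided, power 80%, multiplier 6, floor 150, cap 189; fixed difference 0.65 and dropout f = 0.2; 2019 values SD 1.4, difference 0.8, f = 0.1. Allocation is 1:1:1 (Protocol 9.3), so pooled against placebo is 2:1. Final tests are two-sided at 0.05.

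**Step 1: reproduce the stated power.** With 40 completers per arm, λ = δ / (σ√(1/n₁ + 1/n₂)) and power ≈ Φ(λ − 1.96).
- Pooled, 80 v 40: λ = 0.65 / √(1/80 + 1/40) = 3.357, power 91.9% (noncentral t 91.5%).
- Per dose, 40 v 40: λ = 0.65 / √(2/40) = 2.907, power 82.8% (noncentral t 81.9%).

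The stated ≥90% and ≥80% are right at SD 1.0%. The figures for 189 patients at SD 1.3% (≥80% and ≥69%) also reproduce: 100 v 50 gives 82%, and 50 v 50 gives 70–71%.

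**Step 2: apply the written rule at SD 1.4%.** N = 6 × (1.96 + 0.8416)² × (σ/μ)² / (1 − f), where (1.96 + 0.8416)² = 7.849.

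N = 6 × 7.849 × (1.4/0.65)² / 0.8 = 273, so the rule returns 189. For SDs of 1.35% to 1.45%, N runs from 254 to 293, always above the cap. The printed rule returns 150 only for an SD of 1.04% or less, and reaches 189 at 1.165%.

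The multiplier 6 suits a comparison of one dose with placebo (2 per arm × 3 arms). For pooled against placebo at 2:1 it would be 4.5. That gives 205 at SD 1.4% (190 to 220 over the rounding range), still at the cap.

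**Step 3: see which changed input matters.** N at SD 1.4%, before floor and cap:

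| Difference | Missing | Multiplier 6 | Multiplier 4.5 |
|---|---|---|---|
| -0.65% | 20% (rule) | 273 | 205 |
| -0.65% | 10% | 243 | 182 |
| -0.8% | 20% | 180 | 135 |
| -0.8% | 10% (2019) | 160 | 120 |

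The treatment difference does most of the work. With both inputs changed, the printed formula gives 149 to 172 over SDs of 1.35% to 1.45%, which is compatible with approximately 150. With 4.5 it gives 120, which the floor would lift to 150. The SAP does not say which multiplier was used in 2019.

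**Step 4: power of 150 enrolled at SD 1.4%.** Ranges run from noncentral t to the normal approximation.

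| Difference | Missing | Pooled | Per dose |
|---|---|---|---|
| -0.65% | 20% (80 v 40; 40 v 40) | 66–67% | 54–55% |
| -0.65% | 10% (90 v 45; 45 v 45) | 71–72% | 59–60% |
| -0.8% | 20% | 83–84% | 71–72% |
| -0.8% | 10% | 87–88% | 76–77% |

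Over SDs of 1.35% to 1.45%, the first row spans 63–70% and 51–58%, and the last 85–90% and 74–80%. For comparison, 189 enrolled (150 completers) at SD 1.4% with -0.65% gives 76% pooled and 63–64% per dose.

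**The case against.** The SAP does not hide the changed inputs. It prints them directly after the claim and calls the difference and the missing proportion assumed. It also says the exercise followed regulatory feedback, and Protocol 12.1 says the SAC will document the exact procedure, so a justification may exist outside these documents. Nothing suggests that -0.8% came from unblinded trial data.

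On substance, 150 can be defended. With the 2019 inputs the pooled comparison has 87–88% power, above the re-estimation's 80% target, and the sponsor could have kept 150 on feasibility grounds in any case. The ≥90% and ≥80% figures are printed with their assumptions and are correct under them.

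All of that stands, and it limits the point to how the decision is described. It does not remove the contradiction. The regulatory feedback is cited for carrying out the calculation, not for the two values. The SAP does not say that it departed from the rule printed just above, and it does not give feasibility as the reason for staying at 150. Protocol 12.1 discloses none of the inputs. None of the three planning inputs (SD 1.0%, -0.65%, 20%) was used in 2019, so a similar total does not confirm the original estimate.

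**Conclusion.** The concern holds. At the SAC's SD the pre-specified rule returns 189, whatever the rounding of 1.4% and whether the multiplier is 6 or 4.5. The figure of about 150 depends on replacing both fixed inputs, chiefly the treatment difference, without a stated source. The power printed for 150 patients is right at SD 1.0% but was not updated. At SD 1.4% it is about 67% pooled and 55% per dose with the fixed inputs, and about 88% and 77% with the 2019 inputs.

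The powers are for simple two-sample comparisons among patients with Week 26 data, with missingness equal across arms. No Type I error problem is shown, and enrolling 150 is not itself the fault.

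A smaller inconsistency goes with this. SAP 5.1 and 6.1.2 say the sponsor receives only the recommended sample size, yet SAP 5.1 prints the SD that the SAC supplied.

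**What to change.** 1. In SAP 5.1 and Protocol 12.1, replace the statement that the original estimate was confirmed with wording such as: *With the difference and dropout fixed at -0.65% and 20%, an SD of 1.4% would give the maximum of 189. The 2019 calculation instead used -0.8% and 10% missing [source and reason]; 150 was retained because [reason].* Ideally also state the multiplier used.
2. In the Synopsis, Protocol 12.1 and SAP 5.1, label ≥90% and ≥80% as the original planning values and add: *At SD 1.4%, 150 patients give about 67% pooled and 55% per dose with -0.65% and 20% dropout, and about 88% and 77% with -0.8% and 10% missing.*
3. In SAP 5.1 and 6.1.2, state that the SD was also released to the sponsor.

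The cost is wording in four places and a less favourable power statement. No patients, tests or alpha levels change.
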